16 RANDOMISATION AND BLINDING

16.1 Timing of randomisation

Participants will be randomised once informed consent has been given, eligibility for participation has been confirmed and baseline questionnaires have been completed.

16.2 Randomisation procedure

Participants will be randomised by the local study team via a centralised validated computer randomisation program through a secure (encrypted) web-based service, RRAMP (https://rramp.octru.ox.ac.uk), provided by the Oxford Clinical Trials Research Unit (OCTRU), accessed via the SARONG REDCap study database.

Participants will be randomised in a 1:1 ratio to one of the following treatment arms:

Arm	Details
Follow-up with intensive surveillance	Intensive surveillance (including radiological (CT)
(intervention arm)	scans) every 6 months for 36 months and
	endoscopy at 12 months post-randomisation
Usual care follow-up (control arm)	Standard of care follow-up for 36 months

Upon randomisation of a participant the OCTRU SARONG study office and a member of the site research team will be notified by an automated email.

Full details of the randomisation procedure will be stored in the Randomisation and Blinding Plan in the confidential statistical section of the Trial Master File (TMF).

16.3 Randomisation methodology

Consenting participants will be allocated randomly (1:1) to either the intensive surveillance arm or standard of care.

Randomisation will be performed using a minimisation algorithm to ensure balance between the two treatment groups using stratification factors:

• Recruiting centre

- Age (<50 years, 50-70 years, >70 years)
- Pathological TNM Stage (I & II, III & IV)

The first few participants will be randomised using a simple randomisation schedule, prepared by the trial statistician, to seed the minimisation algorithm, and a non-deterministic probabilistic element will be included to prevent predictability of treatment allocation. The randomisation schedule will be designed by the OCTRU study statistician.

16.3.1 Justification for stratification factors

Patient age and pathological TNM stages are potential confounding factors affecting overall survival (primary outcome of the study), and thus are included within the minimisation algorithm.

16.4 Back-up randomisation procedure

As randomisation is not time-critical there is no back-up randomisation procedure.

17 STUDY ASSESSMENTS/PROCEDURES

The study flow chart can be found in Appendix 1 of this protocol.

Endoscopy and CT scans require hospital attendance, however other assessments could be undertaken electronically/over the telephone.

17.1 Overview

The below table shows scheduled assessments including sampling for the study. Please refer to the Data Management and Sharing plan for more details of clinical visit windows and questionnaire distribution.

	BASELINE			P	OST-RANDO	OMISATION		
	After surgery within		6	12	18	24	30	36
PROCEDURE	12 weeks		Months	months	months	months	months	months
All Participants								
Screening/check eligibility	X							
Informed consent & confirm eligibility	X	Z						
Baseline data collection	Х							
HRQoL questionnaires	x	A	x	x	x	x	x	x
(EQ-5D-5L, EORTC QLQ-C30, EORTC QLQ-OG25, CWS)	^	115	A	~	~	~	~	~
Healthcare Resource Use Questionnaire	X	N	Х	Х	Х	Х	Х	Х
Outcome data collection		DO	Х	Х	Х	Х	Х	Х
Control group (usual care)		AN						
Clinic visit or telephone call ^{\$}	Х	R	Х	Х				
Intervention group (intensive surveillance)								
Clinic visit or telephone call	Х		Х	Х	Х	Х	Х	Х
Endoscopy +/- biopsy^				Х				
CT scan			Х	Х	Х	Х	Х	Х

^ Biopsies will be performed according to each hospital's standard practice where an abnormality is visualised.

^{\$}After 12 months participant will follow standard of care in local centre, either discharge to primary care physician or continued clinical follow-up. Patients in this group will be evaluated for trigger symptoms (described above) in this group.

17.2 Data Collection

17.2.1 Baseline (within 12 weeks postoperatively) data collection

Sourced/collected by local study team Completed at hospital by local study team member from medical notes or with participant		Direct patient report
•	Participant demographics Blood test results Clinical staging results including CT findings before surgery Neoadjuvant therapy utilised Surgery performed and postoperative complications Intended adjuvant therapy	 Health-related quality of life questionnaires* EQ-5D-5L (unmodified) EORTC QLQ-C30 EORTC QLQ-OG25 Cancer Worry Scale (CWS) Healthcare Resource use questionnaire
•	Postoperative complications Pathological staging of cancer	

*QoL questionnaires will be completed prior to randomisation.

17.2.2 Follow-up assessments/subsequent visits

6, 12, 18, 24, 30 and 36 months post-randomisation

So	urced/collected by local study team	Direct patient report
Со	mpleted at hospital by local study team	
me	mber from medical notes or with participant	
٠	Blood test results	 Health-related quality of life questionnaires
•	CT-scan results (intervention arm only)	 EQ-5D-5L (unmodified)
٠	Further radiological or endoscopic	○ EORTC QLQ-C30
	investigations	○ EORTC QLQ-OG25
•	Reason for further investigation (both	○ CWS
	arms)	 Healthcare Resource use questionnaire
•	Locoregional or distant tumour recurrence	
٠	Date of mortality and cause of mortality	
•	Treatment of tumour recurrence	
•	Endoscopy results (Intervention arm only) #	
•	Resource use in secondary care	
# c	ollected at 12 month time-point only	

Questionnaire administration

Questionnaires will be sent at the time points specified above and according to the schedule set out in the Data Management Plan, and with 2 follow up reminders. For participants who have failed to return questionnaires, the central research team will check their clinical status with the local study team and then attempt to obtain the data over the telephone using the relevant script for that questionnaire, detailed below. Participants with limited English who are unable to complete these

over the telephone may be offered additional electronic or postal forms, to complete at home to allow them to access their support networks directly.

EQ-5D-5L: The self-complete version for use in REDCap will be used for participants completing the questionnaire electronically. The self-complete version on paper may also be used. Where participants have failed to return questionnaires, the central research team will check their clinical status with the local study team and then attempt to obtain the data over the telephone using the EQ-5D-5L telephone interviews scripts.

Where necessary, permission for use of all validated questionnaires used in this study have been obtained.

Self-reported Healthcare Resource Use Questionnaire: The Healthcare Resource Use Questionnaire in REDCap will be used for participants completing the questionnaire electronically. The Healthcare Resource Use Questionnaire on paper may also be used. Where participants have failed to return questionnaires, the central research team will check their clinical status with the local study team and then attempt to obtain the data over the telephone.

17.2.3 Endoscopy (intervention/active surveillance arm only)

Participants randomised to the intervention arm (intensive surveillance) will have an upper GI endoscopy with or without biopsy at 12 months post-randomisation. Biopsies will be performed if an abnormality is visualised according to each hospital's standard practice, and as per standard of care pathway.

17.2.4 CT scans (intervention/active surveillance arm only)

Participants randomised to the intervention arm (intensive surveillance) will have a chest, abdomen and pelvis CT scan performed every 6 months for 36 months post-randomisation.

17.2.5 Further endoscopic/radiological investigation – both arms

Participants randomised to either arm will undergo further endoscopic or radiological investigation for cancer recurrence if they report any of the following symptoms during clinical review either within the study or outside of the study as part of normal clinical practice:

- dysphagia to solid food
- dysphagia to liquids
- vomiting
- abdominal pain
- chest pain
- regurgitation of foods
- unexpected weight loss
- progressive hoarseness of voice.

17.3 Withdrawal of Participants

17.3.1 Withdrawal of consent by the participant

Withdrawal of consent means that a participant has expressed a wish to withdraw from the study altogether, or from certain aspects of the study only. The type of withdrawal will be collected on the Withdrawal CRF.

Participants may also be withdrawn from the study (or aspects of the study) by their clinician if they believe the participant needs to be withdrawn.

The Withdrawal CRF should be completed to document the reasons for withdrawal, and state who made the decision to withdraw. Discussions and decisions regarding withdrawal should be documented in the participant's medical notes. Investigators should continue to follow-up any SAEs and should continue to report any SAEs to resolution in the CRF in accordance with the safety reporting section.

Where a participant expresses a wish to withdraw from the study, the study team will determine which aspect(s) of the study the participant wishes to withdraw from; all other aspects of the study/follow-up will be continued. The local study team should discuss with the patient if they accept subsequent data (including routine care data) to be collected as part of the study. This data as a minimum would be data from medical records, ONS and NOGCA for the analysis of mortality as the primary outcome of the trial.

The aspects of the study that the participant may request to withdraw from are as follows:

- No longer willing to receive study intervention
 - participants would have no more CT scans than standard of care, but would continue active follow-up to complete the study questionnaires and allow continued collection of data from medical records that is recorded as part of routine standard care).
- No longer willing to complete study questionnaires
 - this refers to the health-related quality of life questionnaires and Healthcare Resource
 Use questionnaires sent directly to participants by the study office
- No longer willing to have standard of care data from the medical record provided to the study
- No longer willing for standard of care data from Health data providers e.g. NHS digital, to be provided to the study
 - o this refers to data from ONS and NOGCA

Data collected up to the point of withdrawal will be used in the study analysis, or beyond depending on the specific type of withdrawal described above.

17.4 Communication with trial participants by the central trial team

Participants will be notified to completed study questionnaires by e-mail, or where they have selected to receive postal questionnaires these will be posted to the participant. Participants will receive an initial e-mail and up to two reminder messages. Participants that do not complete their study questionnaires may be telephoned by a member of the central study team to collect outcome data.

18 SAFETY REPORTING

The study will be run in accordance with OCTRU's Standard Operating Procedures (SOPs) and operational policies, which all adhere to applicable UK regulatory requirements.

An independent Data and Safety Monitoring Committee (DSMC) and Trial Steering Committee (TSC) will be appointed. The DSMC will monitor data arising from the trial, review confidential interim reports of accumulating data, and recommend whether there are any ethical or safety reasons why the trial should not continue. The TSC will monitor the trial's progress and will provide independent advice. Both committees will comprise independent clinicians, statisticians, health service researchers

and patient representatives. Additionally, the study may be monitored, or audited by sponsor or host sites in accordance with the current approved protocol, GCP, relevant regulations and standard operating procedures.

18.1 Definitions

18.1.1 Safety reporting period

Safety reporting will begin from randomisation and will end when the participant has reached their main follow-up time point at 36 months post-randomisation.

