5 LAY SUMMARY/PLAIN ENGLISH SUMMARY

There are over 15,800 new cases of gullet (oesophageal) or stomach cancer diagnosed every year in the UK, with over 12,300 deaths per year attributed to these cancers. Currently, most patients with cancer of the gullet and stomach are treated with surgery with or without additional chemo- or radio-therapy. In recent years there have been improvements in survival from these two cancers, due to better therapies, less invasive surgery and earlier detection. Despite these improvements, in around two-thirds of patients treated with surgery, the cancer will return and lead to death within three years.

At present there is very little evidence as to how gullet and stomach cancer patients should be followed up after surgery and whether different methods of follow-up could improve survival. Currently, national and international guidelines do not provide consistency in their recommendations for follow-up after surgery.

The SARONG study will investigate if regular radiological scans can lead to earlier detection of a cancer returning, at a stage when it may be more readily treatable. This means that participants who agree to take part will be allocated by chance to either more intensive surveillance (including regular radiological scans and a camera test (endoscopy)) or the current standard of care. The study aims to recruit at least 952 participants in the UK over a 32-month period from at least 24 NHS hospitals. Patients undergoing surgery for gullet or stomach cancer will be invited to participate in the study up to 12 weeks after this surgery.

(i) The intensive surveillance group will receive a review in clinic or by telephone with a member of the surgical team, and a radiological scan at 6, 12, 18, 24, 30 and 36 months after randomisation. They will also receive endoscopy at 12 months after randomisation.

(ii) The standard care group will receive a review in clinic or by telephone at 6 and 12 months. After this they will be either discharged to their local doctor or receive a review in clinic with a member of the surgical team every year.

The main aim of this study will be to determine whether earlier detection of cancer through more intensive follow-up results in improved survival and better quality of life for patients with gullet or stomach cancer.

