10.3 Duration of participant involvement

Participants will be in the study for approximately 36 months from randomisation to last protocol visit. Mortality and recurrence data will be collected for 36 months after the last participant is randomised, this data will be collected from medical records and in the case of all-cause mortality validated against NOCGA and NCRAS.

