18.2 Reporting Procedures

It is important to consider the natural history of oesophago-gastric cancer affecting each participant enrolled, the expected sequelae of the illness, and the relevance of these complications to the study treatment. All eligible participants have a poor prognosis, and due to the complexity of their condition are at increased risk of experiencing multiple adverse events. Consequently, only Serious Adverse Events (SAE) will be recorded in this study. This is limited to serious adverse events, which might reasonably occur as a consequence of the study surveillance (i.e. not events that are part of the natural history of the primary disease process or expected complications of oesophagogastric cancer).

SAEs, as defined above (and unless excluding from reporting – see below), experienced by a participant from randomisation until their completion of the study must be reported in the participant's medical notes, on the study CRFs, and reported to the CTU using the SAE Reporting Form, within 24 hours of observing or learning of the SAE(s). The SAE form will be kept on REDCap to enable direct data entry. All sections of the SAE Reporting Form must be completed. The CTU is automatically notified of the SAE report through the database. A paper SAE form should be used as a back-up if the SAE form is not available electronically.

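### Safety reporting ends at the month-36 time point, when the last surveillance CT is scheduled, so delayed non-fatal SAEs of that scan need not be reported

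*Protocol*

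**What the plan says.** Section 18.1.1 opens safety reporting at randomisation and says that it "will end when the participant has reached their main follow-up time point at 36 months post-randomisation". Section 18.2 words the window differently: SAEs "from randomisation until their completion of the study must be reported". Section 10.3 fixes what completion means for a participant: "Participants will be in the study for approximately 36 months from randomisation to last protocol visit".

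The surveillance schedule ends at the same point. The lay summary gives the intervention arm "a radiological scan at 6, 12, 18, 24, 30 and 36 months after randomisation", and section 17.2.4 has a "chest, abdomen and pelvis CT scan performed every 6 months for 36 months post-randomisation". The table in section 17.1 puts a CT in the 36-month column and leaves the visit windows to a data management plan.

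Section 18.2 limits what is reportable to "serious adverse events, which might reasonably occur as a consequence of the study surveillance". After a participant's month 36, section 10.3 continues only mortality and recurrence data, until 36 months after the last randomisation.

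**The concern.** The SAEs that sites must report are those that surveillance could cause, yet the reporting window closes at the last scheduled surveillance procedure. The month-30 CT has six months of reporting after it and the month-12 endoscopy has 24 months. The month-36 CT has none that is written down.

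A serious event that appears days after the final scan would not have to reach the trials unit. It could then miss the safety review by the DSMC (section 22.4.2) and, if related and unexpected, the report to the ethics committee (section 18.3). The onset window is an obligation on sites that the protocol itself fixes, and an analysis plan cannot recover events that were never collected.

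**Working it through.** The protocol gives no figure for this point, so the check sets the sections side by side and then sizes the last scan round.

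**Where the window ends**

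| Source | What it fixes | End |
|---|---|---|
| 18.1.1 | Safety reporting period | 36-month time point, no lag |
| 18.2 with 10.3 | SAE reporting until the participant's completion | Last protocol visit, about 36 months |
| Lay summary, 17.1, 17.2.4 | Last surveillance CT | 36 months |
| 10.3 | Collection after a participant's month 36 | Mortality and recurrence only |
| 17.3.1 | Following SAEs to resolution | Withdrawal section; concerns SAEs that have already arisen, not new onsets |

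No section adds an interval after the last CT.

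**Size of the last round**

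Inputs: 476 participants in the intervention arm (section 10) and 45% three-year mortality in that arm (section 20.2). Assumptions not in the protocol: constant hazard, every surviving participant attends every scan, and nobody stops scans after recurrence.

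- Proportion alive at scan k (k = 1 to 6, at month 6k): S(k) = 0.55^(k/6).
- Expected scans per round, 476 × S(k): about 431, 390, 353, 320, 289 and 262.
- Last round: 476 × 0.55 = 261.8, about 262.
- All rounds: 476 × [S(1) + … + S(6)] = about 2,044.
- Share in the last round: 261.8 / 2,044.4 = 12.8%.
- Upper reference with no deaths: 476 / (6 × 476) = 476 / 2,856 = 16.7%.
- If 10% of survivors are also lost by month 36 (section 20.2 allows 10% loss): 261.8 × 0.9 = 235.6, about 236 final scans.

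These figures count scans. The protocol gives no SAE rate per CT and no split between immediate and delayed events, so the number of unreported SAEs cannot be derived.

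**The case against.** The strongest reply is that the 36-month time point is a visit, not an instant. The 17.1 table puts the CT, the clinic contact and outcome collection in one 36-month column, and section 17.2.2 collects CT results and further investigations at that visit. A serious reaction to a scan done at the visit is then plausibly inside the window. This stands, and it confines the gap to delayed events and late scans.

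A reader might go further in four ways, none of which the protocol supports.

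- **The final scans have no SAE cover at all.** Immediate reactions are plausibly covered, as above. Whether a scan done some weeks late falls outside depends on visit windows in a plan not shown.
- **Complications of work-up prompted by the last CT are lost because of the cut-off.** Section 10.5.1 sends indeterminate lesions to local protocols, section 18.2 limits reporting to consequences of the surveillance, and section 18.3.1 exempts some sequelae of operations. Whether such complications are reportable after any round is unclear, so the loss cannot be put down to the month-36 cut-off alone.
- **The gap biases the comparison in favour of surveillance.** The cut-off is the same in both arms, control participants also have symptom-triggered investigations, and no SAE comparison is among the outcomes in sections 9.2 and 9.3. Scheduled scans exist in one arm only, so any uncounted scan-related events would fall there, but no size can be given.
- **Sections 18.1.1 and 18.2 contradict each other.** The wording differs, but section 10.3 brings both to about 36 months.

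Deaths after month 36 are still collected until 36 months after the last randomisation. A fatal complication would be counted as a death for all but the last participants randomised, for whom little or no time remains.

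**Conclusion.** The point holds in a limited form. Read as written, the protocol places no obligation to report a delayed, non-fatal SAE of the final surveillance CT, or any non-fatal SAE of a CT done after month 36 if the visit windows permit one. The round concerned is about 13% of surveillance CTs under the stated assumptions and about 17% if nobody dies. This measures exposure without stated follow-up, not harm missed. The primary outcome, all-cause mortality, is untouched. It is a gap in safety collection that is cheap to close, not a threat to the trial's main conclusion.

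**What to change.** Give sections 18.1.1 and 18.2 the same end, applied to both arms: safety reporting continues until a short fixed interval (for example 30 days; the length is the sponsor's choice) after the 36-month time point or the last study CT, whichever is later. The second limb covers a late scan whatever the visit windows say.

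In the same place, state whether SAEs of diagnostic procedures prompted by a study CT are reportable when they occur within that interval. This also settles their status for the earlier rounds.

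The cost is a sentence or two in the protocol and one extra record check per participant. Record review already continues past month 36 for all but the last participants (section 10.3). Safety data for those last participants would close about a month later with a 30-day interval, and section 24.14 already allows time after the last follow-up for data entry and cleaning.

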18.1.2 Adverse Event (AE)

An adverse event is any untoward medical occurrence in a clinical study participant.

Note: An adverse event can therefore be any unfavourable and unintended sign (including an abnormal laboratory finding, for example), symptom or disease temporarily associated with the trial procedures, whether or not considered related to the procedures.

18.1.3 Serious Adverse Event (SAE)

A serious adverse event is any untoward medical occurrence that:

- results in death
- is life-threatening
- requires inpatient hospitalisation or prolongation of existing hospitalisation
- results in persistent or significant disability/incapacity
- may have caused a congenital anomaly/birth defect

Other 'important medical events' may also be considered a serious adverse event when, based upon appropriate medical judgment, the event may jeopardise the participant and may require medical or surgical intervention to prevent one of the outcomes listed above.

Note: The term "life-threatening" in the definition of "serious" refers to an event in which the participant was at risk of death at the time of the event; it does not refer to an event which hypothetically might have caused death if it were more severe.

